7.1.3 Temporary IMP discontinuation

Study participant **must be** TEMPORARILY discontinued from the IMP if any of the following events occur:

1. The study participant develops an event of hypogammaglobulinemia with a serum total IgG of <1g/L irrespective of infection. When the IgG level reaches ≥2g/L, the study participant may be allowed to continue treatment with IMP (see Appendix 13; Section 10.13.1).
2. Symptomatic cases of confirmed COVID-19 infection. The IMP may be restarted if clinically appropriate when signs and symptoms have resolved and in agreement with local guidelines.
3. Study participant has a suspected DIAM. The IMP may be restarted if clinically appropriate when signs and symptoms have resolved. Refer to Section 7.1.4 for permanent discontinuation criteria (criterion #10).

Study participants **may be** TEMPORARILY discontinued from the IMP if the following events occur:

1. The study participant develops a nonserious persisting or recurrent infection with serum total IgG level between ≥1 and <2g/L. Upon resolution of infection and the IgG returning to level of ≥2g/L, the study participant may be allowed to resume treatment with the IMP (see Appendix 13; Section 10.13.1).
2. Asymptomatic or suspected cases of COVID-19 infection. The IMP may be restarted when clinically appropriate as deemed by the Investigator and in agreement with local guidelines.
3. Study participant has a moderate to severe infection (Grade 2 to 3) that may or may not result in hospitalization, unless the **discontinuation criterion #3** is met. Decision to start a new treatment cycle should be based on careful evaluation by the Principal Investigator of the Benefit-Risk for the individual study participant and provided a full recovery from infection has occurred, an acceptable level of total IgG (≥2g/L) has been reached and no other discontinuation criteria were met.

The Investigator should discuss with the Medical Monitor and/or Sponsor's study physician prior to reinitiating the IMP. As appropriate, virtual assessments could continue (eg, AE collection, patient-reported outcome [PRO] assessments as per contingency measures described in Section 8).

If IMP treatment is resumed, continue the next dose as previously scheduled. No "make up" dose is permitted.

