9. Study participant is treated with rescue therapy (IVIg, SCIG, PEX, or iv corticosteroids; see Section 6.5.4) during the Treatment Period. Those patients who received rescue therapy during the observation or no treatment with rozanolixizumab periods may continue in the study at the investigator's discretion and after discussion with Medical Monitor and/or UCB Study Physician. The following cycle of rozanolixizumab should in general not start earlier than 4 weeks following the last dose of IVIg, SCIG, or iv corticosteroids or the last PEX

session, unless there is a medical reason, and an earlier treatment initiation is being considered █ for the study participant as agreed upon with the Medical Monitor and/or UCB Study physician.

10. Study participant has a recurrence of aseptic meningitis (see also Appendix 14 [Section 10.14]).

Study participants **may** permanently discontinue rozanolixizumab **and** move into the Observation Period at the discretion of the Investigator, Medical Monitor, and Study Physician if any of the following events occur:

1. Study participant is noncompliant with the study procedures or medications in the opinion of the Investigator.
2. Study participant takes prohibited concomitant medications as defined in this protocol.

Investigators should contact the Medical Monitor, whenever possible, to discuss the withdrawal of a participant in advance. Investigators should attempt to obtain information on study participants in the event of withdrawal (eg, reason for withdrawal, any safety information).

In the event of study participant early withdrawal, the scenarios as described in Section 4.4 need to be considered.

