All procedures related to the diagnosis, treatment, and investigation of meningitis should be recorded in the eCRF, and preliminary data should be included on the SAE form used for reporting the event as an AESM within 24 hours (ie, preliminary data reported on the first reporting may not have CSF results yet, but the reporting should occur as soon as there is a suspected diagnosis. Full results should be communicated in subsequent exchanges with the sponsor).

Treatment must be temporarily held if a participant has a diagnosis of suspected meningitis of any cause until the diagnostic workup is complete. Based on CSF findings, negative cultures, absence of other disease causes, and relationship with IMP, a diagnosis of DIAM can be made. If deemed appropriate by the Investigator and agreed upon by the participant and the Sponsor, the

study treatment can resume upon the complete resolution of symptoms. The benefit and risk of the treatment should be carefully considered prior to reinitiating the IMP. If a participant experiences a second episode of similar symptoms suggestive of DIAM, then the participant must permanently discontinue the IMP.

Participants experiencing an event of DIAM should be strongly encouraged to remain in the study regardless of IMP discontinuation. This will allow for monitoring and follow-up of the participant including a complete neurological exam on subsequent physical examinations. Longer term follow-up on any AEs related to DIAM that are ongoing may be warranted until resolution.

Associated symptoms with aseptic meningitis should be managed at the Investigator's discretion.

Severe and/or serious headache

Based on current available clinical data, headache is the most commonly reported ADR in study participants treated with rozanolixizumab. Study participants should be well informed of this potential ADR and should be instructed on how to manage it.

Determination of the severity of headache will be consistent with National Cancer Institute Common Terminology Criteria for Adverse Events (CTCAE) version 5.0. Severe headache is defined as severe pain limiting self-care activities of daily living (ADL). Self-care ADL refers to bathing, dressing and undressing, feeding self, using the toilet, and taking medications.

In the event of a headache, the Investigators should take the medical history of previous headaches, concomitant medication, and co-morbidities (eg, asthma) in consideration.

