If the severe and/or serious headache is initially reported at a home visit or during a telephone call, the study participant should be evaluated by a healthcare professional as soon as possible for further investigations. Study participants should be monitored for signs and symptoms suggestive of CNS involvement and evaluated immediately if other causes (eg, meningitis, intracranial bleeding) are suspected (please see Section 1.3.1 [Table 1-6]). In addition, samples for exploratory safety biomarkers should be collected for study participants experiencing severe or serious headache when possible. These investigations will be performed to further understand the mechanism of headaches in the study participants.

If deemed appropriate by the Investigator and agreed upon by the study participant and the Sponsor, the study treatment can resume upon the resolution of the severe and/or serious headache event. The benefit and risk of the treatment should be carefully considered prior to reinitiating the IMP.

Headaches will be treated as clinically indicated according to national guidelines. It is recommended that the study participants have an analgesic available in case of headache with the instruction for frequency and dosage provided by a healthcare professional. The analgesic can be started at the early onset of headache. Study participants experiencing any treatment-related headache will be followed until resolution of the event.

Prophylactic treatment of headaches may be permitted for study participants who have experienced previous episodes of treatment-related headache after discussion with the Medical Monitor. The benefit risk of continuing treatment with IMP and chronic prophylactic with analgesics must be carefully evaluated by the Investigator.

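### Sections 7.1.3 and 7.1.4 and Appendix 14 state different mandatory triggers for holding and permanently stopping rozanolixizumab in suspected aseptic meningitis, and none is given precedence

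*Protocol*

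**What the plan says.** **Permanent stop.** Criterion 10 in the mandatory list of Protocol Section 7.1.4 reads "Study participant has a recurrence of aseptic meningitis (see also Appendix 14 [Section 10.14". Appendix 14 (Section 10.14) reads "If a participant experiences a second episode of similar symptoms suggestive of DIAM, then the participant must permanently discontinue the IMP".

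**Hold.** Item 3 of the mandatory list in Section 7.1.3 reads "Study participant has a suspected DIAM. The IMP may be restarted if clinically appropriate when signs and symptoms have resolved", and then refers the reader to criterion 10. Appendix 14 reads "Treatment must be temporarily held if a participant has a diagnosis of suspected meningitis of any cause until the diagnostic workup is complete".

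**Restart.** Section 7.1.3 adds, for all its holds, "The Investigator should discuss with the Medical Monitor and/or Sponsor's study physician prior to reinitiating the IMP". Appendix 14 says that "study treatment can resume upon the complete resolution of symptoms", provided the Investigator considers it appropriate and both the participant and the Sponsor agree.

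**Infection.** The optional list in Section 7.1.3 allows a hold when "Study participant has a moderate to severe infection (Grade 2 to 3) that may or may not result in hospitalization", unless criterion 3 of Section 7.1.4 applies. Criterion 3 names infectious meningitis during a treatment period as a reason for permanent stop.

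**Headache.** Appendix 14 says that "the study treatment can resume upon the resolution of the severe and/or serious headache event", again with participant and Sponsor agreement. Neither list in Section 7.1.3 mentions headache, item 7 of Section 7.1.4 is blank, and Section 6.6 deals only with the dose level at the start of a cycle.

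**The concern.** Suspected aseptic meningitis is one of the two adverse events of special monitoring (Section 8.3.7). A site that meets a case must decide whether to hold dosing, when dosing may restart, and whether it must end for good. The protocol answers each question twice, in mandatory terms, with different triggers.

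The first stake is re-dosing: participants with the same event could be treated differently according to which text the site applied. The second is classification. Withdrawal of IMP because of a TEAE is one of the two primary safety endpoints (Protocol Section 3; SAP Section 2.2.1.1), and SAP Section 8.2.2 tabulates permanent and temporary withdrawal separately. The same clinical event could fall in either row.

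**Working it through.** The protocol gives no figure to reproduce. The check sets the passages side by side and follows specific cases through both texts.

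**1. Permanent-stop trigger.**
- Criterion 10 names a condition. It does not say whether a suspected recurrence is enough, and it is not limited to drug-induced cases.
- Appendix 14 names symptoms and ties them to DIAM.
- Section 7.1.3 item 3 and Section 8.3.7 both use the qualifier for suspicion. Criterion 10 omits it, so a site could reasonably take it to need a diagnosis.

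*Case A: an undiagnosed second episode.* A first episode is judged DIAM and dosing is restarted. A second episode is suggestive, but cerebrospinal fluid is not obtained or is non-diagnostic. This is foreseeable: Appendix 14 treats DIAM as a diagnosis of exclusion, asks only that a full workup be strongly considered, and leaves the choice of procedures to the Investigator or treating physician.
- Under Appendix 14, permanent stop is mandatory.
- Under Section 7.1.4, if criterion 10 is read as needing a diagnosis, it is not met. Section 7.1.3 item 3 then gives a hold with possible restart.
- Under Section 7.1.4, if suspicion is enough, criterion 10 agrees with Appendix 14.

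*Case B: a recurrence with a non-drug cause.* Aseptic meningitis recurs and is attributed to something other than the drug.
- Criterion 10 is met on its wording.
- The second-episode sentence in Appendix 14 is not plainly met, because it concerns DIAM.

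The two triggers therefore differ in both directions.

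**2. Hold trigger.**

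*Case C: a suspected non-drug cause.* A specific infectious meningitis is suspected and the workup is open.
- Under Appendix 14, the hold is mandatory until the workup is complete.
- Under Section 7.1.3, item 3 does not apply if the suspicion is not of DIAM. What remains is the optional infection hold.
- If infectious meningitis is then established during a treatment period, criterion 3 applies.

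The difference is confined to the period before diagnosis. Dosing is weekly, so a scheduled infusion can fall within it.

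**3. Restart.**

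| | Section 7.1.3 | Appendix 14 |
|---|---|---|
| Symptoms | resolved | completely resolved |
| Judgement | clinically appropriate | appropriate in the Investigator's view |
| Others involved | discussion with Medical Monitor and/or study physician | agreement of participant and Sponsor |

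The contrast is slight: discussion against agreement, and resolution against complete resolution.

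**4. Headache.** Neither text has a permanent-stop rule and neither states a hold trigger. Appendix 14 has only a resume condition. This is a missing statement, not two competing rules.

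**5. Size.** The documents give no rate for a second episode. Appendix 14 reports only a few DIAM cases across the whole programme. Case A also needs a first episode, a restart and a second, undiagnosed episode. As a scale, assume that all of the approximately 200 participants are dosed. One reclassified participant then moves a pooled percentage by 1/200 = 0.5 percentage points. If a dose column held half of them, the shift would be 1/100 = 1.0 point.

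**The case against.** The strongest reply is that the passages form a chain. Section 7.1.3 item 3 sends the reader to criterion 10, criterion 10 sends the reader to Appendix 14, and Section 8.3.7 names Appendix 14 as the place for AESM management. On this view Section 7.1 is the short rule and the appendix is the operative detail. Criterion 10 never says that a diagnosis must be confirmed, so Case A depends on one reading of it. This softens the point, but following the chain takes the site to a second mandatory rule with a different trigger, and no precedence is stated.

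A second reply is that, because DIAM is a diagnosis of exclusion, an undifferentiated meningitis in a treated participant can count as suspected DIAM until the workup ends. That is fair and narrows Case C to episodes where another cause is suspected from the outset. Criterion 3 and the optional infection hold narrow it further, but neither is a mandatory hold during the workup.

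Third, all analyses are descriptive (SAP Section 4.6) and the events are rare, so no visible effect on the primary endpoint has been shown. That stands.

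A reader might also infer that the two texts set conflicting hold and stop rules for headache. The documents do not support this. Silence in Section 7.1.3 does not require the next infusion to go ahead, and the resume sentence in Appendix 14 fits a discretionary interruption. Section 2.3 calls headache the most common adverse drug reaction but adds that most were mild to moderate, whereas the AESM covers only severe and/or serious headache.

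**Conclusion.** The inconsistency is real for suspected aseptic meningitis. The permanent-stop and hold triggers differ materially, and the restart conditions differ slightly. Sites may handle the same event differently; the documents do not show that they will. The conclusion rests on the absence of any precedence statement and, for Case A, on criterion 10 being open to a reading that needs a diagnosis.

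The effect on the withdrawal endpoint is probably small, since few events are expected. The reason to act is consistent re-dosing after a possible recurrence, together with clean classification of those few events. For headache the finding is only that a resume condition stands without a stated hold.

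**What to change.** Reconcile Section 7.1.3 item 3, Section 7.1.4 criterion 10 and Appendix 14 so that a single wording settles:

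- the event that triggers a hold;
- the restart conditions, and whose discussion or agreement is needed;
- the event that triggers permanent stop, including whether suspicion is enough and whether it is limited to drug-induced cases.

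The other passages should cite that wording and not restate it. In the same edit, make clear whether a hold is intended for severe and/or serious headache. Which wording stands is a clinical decision for the sponsor's medical team.

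The cost is a protocol text change in these passages. It needs no new procedures, data or participants, and the tabulations in SAP Section 8.2.2 can stay as they are.

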7.2 Participant discontinuation/Withdrawal from the study

Participants are free to withdraw from the study at any time, without prejudice to their continued care.

Study participants **must** be withdrawn from the study if any of the following events occur:

1. Study participant withdraws his/her consent.
2. The Sponsor or a regulatory agency requests withdrawal of the study participant.
3. There is confirmation of a pregnancy during the study, as evidenced by a positive pregnancy test.
4. Study participant has active suicidal ideation as indicated by a positive response (Yes) to either Question 4 or Question 5 of the "Since Last Visit" version of the C-SSRS. The study participants should be referred immediately to a Mental Healthcare Professional.

A participant **may** withdraw from the study at any time at his/her own request, or may be withdrawn at any time at the discretion of the Investigator for safety, behavioral, compliance, or administrative reasons.

If the study participant withdraws consent for disclosure of future information, the Sponsor may retain and continue to use any data collected before such a withdrawal of consent.

If a study participant withdraws from the study, he/she may request destruction of any samples taken and not tested, and the Investigator must document this in the site study records.

See the Schedule of Activities (Section 1.3) and Section 4.4 for data to be collected at the time of study discontinuation and follow-up and for any further evaluations that need to be completed.

Investigators should contact the Medical Monitor, whenever possible, to discuss the withdrawal of a study participant in advance.

7.3 Lost to follow up

A participant will be considered lost to follow-up if he or she repeatedly fails to return for scheduled visits and is unable to be contacted by the study site.

The following actions must be taken if a participant fails to return to the clinic for a required study visit:

- The site must attempt to contact the participant and reschedule the missed visit as soon as possible and counsel the participant on the importance of maintaining the assigned visit schedule and ascertain whether or not the participant wishes to and/or should continue in the study.
- Before a participant is deemed lost to follow up, the Investigator or designee must make every effort to regain contact with the participant (at least 1 phone call and 1 written message to the participant), and document his/her effort (date and summary of the phone call and copy of the written message in the source documents), to complete the final evaluation. All results of these evaluations and observations, together with a narrative description of the reason(s) for removing the participant, must be recorded in the source documents. The eCRF must document the primary reason for withdrawal.

Should the participant continue to be unreachable, he/she will be considered to have withdrawn from the study with a primary reason of lost to follow-up documented in the eCRF.

This document cannot be used to support any marketing authorization application and any extensions or variations of marketing authorization. PUBLIC COPY

8 STUDY ASSESSMENTS AND PROCEDURES

Study procedures and their timing are summarized in the Schedule of Activities (Section 1.3).

Protocol waivers or exemptions are not allowed.

Immediate safety concerns should be discussed with the Sponsor immediately upon occurrence or awareness to determine if the participant should continue or discontinue study treatment.

Adherence to the study design requirements, including those specified in the Schedule of Activities (Section 1.3), is essential and required for study conduct.

All screening evaluations must be completed and reviewed to confirm that potential participants meet all eligibility criteria. The Investigator will maintain a screening log to record details of all participants screened and to confirm eligibility or record reasons for screening failure, as applicable.

Procedures conducted as part of the participant's routine clinical management (eg, blood count) and obtained before signing of the ICF may be utilized for Screening or Baseline purposes provided the procedures met the protocol-specified criteria and were performed within the time frame defined in the Schedule of Activities (Section 1.3).

An Unscheduled Visit can be conducted at the discretion of the Investigator (eg, due to an AE).

During the Unscheduled Visit, the following assessments will be performed:

- AE reporting
- Concomitant medications
- Review of withdrawal criteria
- Physical examination
- Vital signs

Blood samples for PK, IgG, hematology, biochemistry, other laboratory testing and assessments may be performed as clinically indicated at the discretion of the Investigator.

Repeat or unscheduled samples may be taken for safety reasons or for technical issues with the samples.

Some study-specific investigations may not be conducted according to the study protocol during a pandemic or other exceptional circumstances (eg, hurricanes) due to the need to implement safety measures and guidance from regulatory authorities. In such a situation, which may be accompanied by local or global containment or other measures, sites may need to prohibit access to study participants and study-related personnel. Study participants visits to the study site may be replaced by contingency measures. These measures are primarily established to ensure the safety of study participants during the course of the study and to maintain the study participants treatment schedule, if the Investigator considers it appropriate. These measures include but are not limited to virtual visits or home-nursing visits replacing site visits, eg, telemedicine contacts or home-nursing visits when treatment and/or blood sampling is scheduled. The contingency measures are described in a contingency plan and will be implemented as required.

8.1 Efficacy assessments

Planned timepoints for all efficacy assessments are provided in the Schedule of Activities (Section 1.3).

8.1.1 MGFA Classification

The Investigator will classify the study participant's MG using the MGFA Clinical Classification ([Jaretszki et al, 2000](#)). This is a 5-stage classification (I to V), with a higher class indicating more severe disease. To be eligible for this study, a participant with a gap period must be graded MGFA CLASS II to IVa at Visit 1, as per inclusion criteria (see Appendix 12 [Section 10.12]).

8.1.2 Quantitative Myasthenia Gravis scale

For assessment of the QMG scale, Investigators or qualified designee will follow the MGFA's QMG Manual instructions. Clinical personnel must complete mandatory training to assess study participants' QMG score (details are provided in the Study Procedures Manual). If not medically appropriate, then the treatment can be continued but the testing should be performed as best as possible at the same timeframe post last acetylcholinesterase AChE inhibitor dosing for each evaluation during the study. Study participants should not take pyridostigmine (or other AChE inhibitor medication) from midnight before testing when medically safe to do so to standardize testing (ie, if AChE inhibitors cannot be stopped). The scale tests 13 items, including ocular and facial involvement, swallowing, speech, limb strength, and forced vital capacity (FVC). For the assessment of FVC, the same spirometer should be used each time a study participant is tested, and if possible, the same person should carry out the assessment. The QMG is a validated assessment ([Barnett et al, 2012](#)), with a higher score indicating more severe disease. Scoring for each item ranges from no weakness (0) to severe weakness (3), with an overall score range from 0 to 39. A 3-point change in the total score is considered clinically relevant. Where possible, the same person should carry out the assessment at each visit.

